## 5.4 Statistical methodology and assumptions

### 5.4.1 Analysis of continuous data

#### 5.4.1.1 Summary statistics for continuous data

Summary statistics (including N, mean, standard deviation, minimum, lower quartile, median, upper quartile, maximum) will be provided for continuous data by visit and treatment group.

#### 5.4.1.2 Non-parametric analysis of covariance

Certain continuous endpoints will be analyzed with an ANCOVA model. The model will include factors and covariates as specified for the respective analyses. The SAS code below outlines a template for the analysis where factors and covariates can be added or removed as required.

SAS code example:

```
proc mixed data=mydata;
    class TRT01PN;
    model CHG = TRT01PN BASE / s ddfm=kr;
    lsmeans TRT01PN / diff cl;
run;
```

A non-parametric ANCOVA model ([Koch 1998](#)) will be used as sensitivity analysis for certain binary endpoints and also for continuous endpoints that risk having a large deviation from a normal distribution.

The macro NParCov3 will be used ([Zink 2012](#)). Input dataset to the macro should only contain the two treatments to be compared and only data from one visit.

The macro call will follow the below templates where covariates (in numeric format only) may be added or removed as required (max one strata variable can be specified).

### For continuous variables

```
%nparcov3(outcomes=outcome, covars=cov1 cov2, c=1, hypoth=alt, strata=strata,
trtgrps=treatment, transform=none, combine=first, dsnin=, dsnout=out);
```

Data sets “\_out\_deptest” and “\_out\_ci” will be automatically created by the macro and contains the following:

- “\_out\_deptest” provides estimate and p-value for the treatment difference, and
- “\_out\_ci” provides a 95% confidence interval for the treatment difference.

## 5.4.2 Analysis of binary and categorical data

### 5.4.2.1 Summary statistics for binary and categorical data

Summary statistics for discrete variables will be presented in contingency tables and will include count and frequency in each category. If applicable, confidence intervals will be derived as well based on the score method including continuity correction ([Newcombe 1998](#)):

With  $z$  as  $(1-\alpha/2)$ -quantile of the standard normal distribution (SAS:  $z=\text{probit}(1-\alpha/2)$ ),  $n$  as total number of subjects (i.e., number of subjects in the denominator),  $p$  as estimated crude incidence (number of subjects with event /  $n$ ) and  $q = 1-p$

Then the lower limit is

$$L = 100 \times \max \left( 0, \frac{2np + z^2 - 1 - z \sqrt{z^2 - 2 - \frac{1}{n} + 4p(nq + 1)}}{2(n + z^2)} \right)$$

and the upper limit is

$$U = 100 \times \min \left( 1, \frac{2np + z^2 + 1 + z \sqrt{z^2 + 2 - \frac{1}{n} + 4p(nq - 1)}}{2(n + z^2)} \right).$$

Note: If  $L > 100 \times p$  then  $L = 100 \times p$  and if  $U < 100 \times p$  then  $U = 100 \times p$ .

### 5.4.2.2 Logistic regression

Certain binary outcome variables, e.g., response outcomes, will be evaluated using a logistic regression model. The model will include factors and covariates as specified for respective analysis. The marginal standardization method will be used to calculate the mean response rate in each treatment group as well as their difference. This method uses the same fitted logistic model, but involves using the model to predict, for each patient in the study, the mean outcome assuming assignment to each particular treatment group in turn, assuming each patient's

observed values for the other baseline covariates (i.e., baseline score). Averaging these predictions for each treatment group provides the estimate of the mean response rate for each treatment group. Then the difference will be derived based on the estimated mean response rates comparing secukinumab and GP2017 arms. The SAS code below outlines a template for the analysis where covariates can be added or removed as required:

The macro Margins ([Predictive margins and average marginal effects](#)) will be used.

SAS code example as the following,

```
%Margins(data = mydata,  
         class = treatment,  
         response = response,  
         roptions = event='1',  
         model = treatment baseline_score,  
         dist = binomial,  
         margins = treatment,  
         options = cl diff)
```

For cases where the convergence status indicates that the model did not reach appropriate convergence (conv\_status is not 0), no risk difference or p-value will be presented from that model.

However, if the issue relates to the primary timepoint of Week 104 then the following steps will be followed:

1. Remove *baseline\_score* from the model. If there are still issues perform step 2
2. Use Fisher's exact test as described below.

When Fisher's exact test is applied, only a p-value for a test of equal response in the two groups can be obtained (no risk difference or confidence intervals can be estimated.)

```
ods output fishersexact=fisher;  
proc freq data=mydata;  
  by visit;  
  table treatment*response / fisher;  
run;
```

Input dataset should only contain data from the two treatment groups to be compared.

### 5.4.3 Imputation methods

#### 5.4.3.1 Tipping point

The goal of the tipping point analysis is to identify assumptions about the missing data and presumed non-response under which the conclusions change, i.e., under which there is no longer evidence of a treatment effect. Then, the plausibility of those assumptions can be discussed.

### For binary variables

Defining all cases with missing data at a specific visit as uncertain cases (i.e., the subject could be either a responder or a non-responder) the following notations are made for a comparison of two treatment regimens:

$R_i$ : Number of observed responders from subjects randomized to regimen  $i$

$NR_i$ : Number of observed non-responders from subjects randomized to regimen  $i$

$M_i$ : Number of uncertain response cases from subjects randomized to regimen  $i$

Where  $i=1, 2$  denotes the two regimens to be compared.

A Chi-square test can now be performed comparing the two regimens for each possible combinations of uncertain response. Table 16-3 shows an outline of all the possibilities for the comparisons, where  $J_i$  takes values from 0 to  $M_i$  for regimen  $i$ .

**Table 5-5** Counts in tipping point analysis

Response	Regimen 1 (N= $N_1$ )	Regimen 2 (N= $N_2$ )
Yes (responder)	$R_1 + J_1$	$R_2 + J_2$
No (non-responder)	$NR_1 + (M_1 - J_1)$	$NR_2 + (M_2 - J_2)$

SAS code for Chi-square test of a specific assignment of uncertain cases:

```
ods output chisq=chisquare;
proc freq data==;
table treatment*response / chisq;
weight n;
run;
```

The input dataset should only include the two regimens to be compared. Number of subjects included in each of the four cells of Table 16-3 (e.g.,  $R_1 + J_1$ ) is denoted by  $n$ .

In order to also take covariates into consideration a logistic regression model may also be performed for selected combinations of response distributions (e.g. worst case scenario where  $J_1=0$  and  $J_2=M_2$ ).

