### 1.1 Study design

This multicenter study uses a randomized, partially-blinded, active-controlled, parallel-group design in subjects with AS. A screening period (SCR) of up to 10 weeks before randomization will be used to assess eligibility followed by 104 weeks of treatment. Two follow-up visits at Weeks 112 and 120 will occur thereafter.

At baseline (BSL), approximately 837 subjects whose eligibility is confirmed will be randomized to one of three treatment groups (1:1:1).

- Group 1: secukinumab 150 mg [1 x 1.0 mL s.c. plus placebo (1 x 1.0 mL s.c.)] at BSL, Weeks 1, 2 and 3, followed by administration every four weeks starting at Week 4
- Group 2: secukinumab 300 mg (2 x 1.0 mL s.c.) at BSL, Weeks 1, 2 and 3, followed by administration every four weeks starting at Week 4
- Group 3: GP2017 (adalimumab biosimilar) 40 mg (1 x 0.8 mL s.c.) at BSL followed by administration every two weeks starting at Week 2

Although study treatment (secukinumab vs GP2017) will be provided in an open-label fashion to the subjects, secukinumab study treatment will be blinded to the dose. Subjects in groups 1 and 2 will know that they are on secukinumab, but will be blinded to which treatment group and will not know whether they are receiving secukinumab 150 mg or 300 mg. Subjects in the GP2017 treatment group will know that they are receiving GP2017 (adalimumab biosimilar) 40 mg. Investigators and study site staff will be blinded in the same manner.

The primary endpoint analysis may be performed after all subjects complete the assessments associated with the primary endpoint visit (Week 104) in order to support regulatory filing. The final analysis will be conducted after all subjects complete the study at Week F120.

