Missing Week 104 data due to an incomplete number of interpretable locations for a given subject will be imputed using the same imputation model as described above but based on the observed data of all subjects who provided Week 104 data and based on the observed data of the given subject.

In this way multiple complete data sets are created and for each of these completed datasets the response rate will be calculated and then combined using Rubin's rule.

The potential sparsity of the retrieved data may preclude fitting the proposed model to impute the subjects with missing X-ray data at Week 104. In this case, a fallback approach will be utilized.

In case of low sample size of the retrieved dropout data (< 8 for any treatment group), the imputation model can lead to unstable imputations. In this case imputations will be performed based on a model without treatment as a covariate.

$$pi = \text{logistic}(\text{beta1} + \text{beta4} * \text{sqrt}(\text{base\_stand}) + \text{beta5} * \text{slope\_stand})$$

In case there are less than 8 retrieved dropout patients overall, the same imputation model as above will be used (without treatment as a covariate) but based on all patients (not only retrieved dropout patients).

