## 3 Sample size calculation

An overall type I error (2-sided) of 5% will be used to control type I error. A total of 279 subjects per group is deemed appropriate to achieve adequate power for the primary and secondary endpoints for this study.

Based on the modeling of data from an unpublished non-interventional study that compared a blinded re-read of radiographic x-ray images from the secukinumab phase III AS study CAIN457F2305 (MEASURE 1) (Braun 2016) and a historical cohort of AS subjects treated with NSAIDs only (ENRADAS), a no progression rate of 66% for secukinumab-treated subjects and 51% for NSAIDs-treated subjects at Week 104 were calculated. Published data for adalimumab-treated AS subjects compared to a cohort of AS subjects treated only with NSAIDs (OASIS) showed no difference in change from baseline in mSASSS at Week 104 (van der Heijde 2009). Therefore, the 51% no progression rate calculated from the subjects who took NSAIDs will be used for GP2017 (adalimumab biosimilar). Assuming 80% of subjects will complete the 2-year study treatment period and provide both baseline and Week 104 evaluable radiographic films with a 66% no progression rate at Week 104 and assuming subjects who discontinue study treatment will have a 51% no progression rate at Week 104, a new no progression rate of 63% for secukinumab was calculated using the definition of the estimand. Therefore, a no progression rate of 63% for secukinumab and 51% for GP2017 were used as assumptions to calculate the sample size using a two-group Chi-square test of equal proportion (nQuery Advisor 7.0) with approximately 73% power at  $\alpha=0.025$ . And the power to reject at least one hypotheses using the Hochberg procedure is 88%.

Analysis of an unpublished Phase III study showed a change from baseline in mSASSS at Week 104 with a mean of 0.52 and standard deviation of 2.5 for secukinumab subjects. With a sample size of 279 subjects in each treatment group, a treatment difference of 0.58 (i.e., assuming GP2017 has a mean of 1.1 and the same standard deviation) yields approximately 68% power at  $\alpha = 0.025$ .

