### For continuous variables

Tipping point to compare each AIN group with the GP2017 group will be performed as follows:

- 1) For any patient  $i$  randomized to the AIN group with an imputed mSASSS value resulting in a change from baseline value in mSASSS at Week 104  $CB_{i,mSASSS}$ , let  $CB_{i,mSASSS}^{tipping} = CB_{i,mSASSS} + d$
- 2) For any patient  $j$  randomized to the GP2017 group with an imputed mSASSS value resulting in a change from baseline value in mSASSS at Week 104  $CB_{j,mSASSS}$ , let  $CB_{j,mSASSS}^{tipping} = CB_{j,mSASSS} + b$
- 3) Let  $d = -1, -2/3, -1/3, \dots, 2$  and  $b = -1, -2/3, -1/3, \dots, 2$

- 4) For each combination, repeat the same ANCOVA analysis with the same model used in the primary analysis and the newly computed changes from baseline
- 5) Identify the values of  $d$  and  $b$  that reverts significance
- 6) A different range of values for  $d$  and  $b$  can be used if no tipping point was identified or if it helps the clinical interpretation

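### The binary tipping-point grid uses an unpooled, unadjusted chi-square test, so its boundary is not where the primary conclusion would change

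*SAP*

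**What the plan says.** **Primary analysis.** SAP 2.5.2 and 5.4.2.2 specify logistic regression with treatment and baseline mSASSS, reported as a difference in marginal proportions. SAP 2.5.3 imputes missing Week 104 outcomes mainly from patients who stopped treatment but still had a Week 104 film (retrieved dropouts). Results from the completed datasets are "combined using Rubin's rule". SAP 5.4.3.2 sets 100 completed datasets.

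**Role of the tipping point.** It is the first sensitivity analysis listed for the primary endpoint in SAP 2.5.4. SAP 2.6.4 carries it over to absence of new syndesmophytes, the endpoint of H5 and H6. SAP 5.4.3.1 gives its goal as to "identify assumptions about the missing data and presumed non-response under which the conclusions change".

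**Binary version.** Missing cases in each arm are set to every possible responder count, from none to all. On each resulting 2x2 table, "A Chi-square test can now be performed comparing the two regimens". There is no covariate, imputation draw or pooling, and no significance level is stated. A logistic model is optional and only for selected combinations; pooling is not mentioned for it.

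**Continuous version.** The same section adds arm-specific shifts to the imputed changes in mSASSS and then says to "repeat the same ANCOVA analysis with the same model used in the primary analysis".

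**The concern.** A tipping-point analysis should start at the primary result and show how far the missing-data assumption must move before that result is lost. The binary grid has a different origin. Its central cell, where the fills equal the mean imputed responder counts, treats those fills as observed and leaves out the between-imputation variance that Rubin's rules add. It also omits the baseline covariate. The central cell therefore need not reproduce the primary p-value, and the reported boundary need not be where the trial's conclusion changes.

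At stake is how robust the primary and syndesmophyte results are reported to be. The continuous version in the same section already works from imputed values and the endpoint's own model.

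**Working it through.** **Inputs from SAP section 3.** 279 per arm; "a no progression rate of 63% for secukinumab and 51% for GP2017 were used as assumptions to calculate the sample size"; 80% completing, so 0.20 × 279 ≈ 56 discontinuers per arm; a 51% rate in discontinuers.

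**The plan's own figure.** A two-sided chi-square at 0.025 with 279 per arm and 63% versus 51% has 73.4% power, against 73% stated. It reproduces and is not in dispute.

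**Formulas.** With m missing per arm, let π be an arm's imputation response rate, drawn from its posterior given the retrieved dropouts.
- Within-imputation variance: W = p1(1−p1)/279 + p0(1−p0)/279.
- Between-imputation variance: B = 2[m²·Var(π) + m·E{π(1−π)}]/279².
- Total: T = W + 1.01·B for 100 imputations.

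The prior on each arm's log-odds is normal with mean 0. SAP 2.5.3 gives it a standard deviation of 2, and the template in 5.4.3.2 a variance of 2, so both were run. Baseline and slope effects are set to zero. P-values use the normal reference and the tipping threshold is 5%.

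**Example (assumed counts).** 39 missing and 16 retrieved per arm, 8 of the 16 being responders. With SD 2, Var(π) = 0.01384 and E{π(1−π)} = 0.2362. Then B = 2(1521 × 0.01384 + 39 × 0.2362)/77841 = 0.000778.

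*Observed responders 150 versus 124.*
- Central cell (20 of 39 in each arm): 170 versus 144 of 279, z = 2.22, p = 0.026. With GP2017 held there, it tips at 16 secukinumab fills.
- Pooled (mean fill 19.5): difference 26/279 = 0.0932; W = 0.001750; T = 0.001750 + 1.01 × 0.000778 = 0.002535; SE 0.0504; z = 1.85; p = 0.064 (0.063 with variance 2). The result is already non-significant with no shift.

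*Observed responders 158 versus 124.*
- Central cell p = 0.0036. The grid tips at 8 of 39 secukinumab fills (21%).
- Pooled p = 0.015. Shifting the secukinumab log-odds down tips it at about −0.8, a mean of about 12 of 39 (31%).

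**At the planned rates.** Chi-square SE = √(2 × 0.57 × 0.43/279) = 0.0419, z = 0.12/0.0419 = 2.86, p = 0.004 whatever the number of retrieved dropouts. Taking W = 0.0419²:

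| Retrieved per arm | Missing | √B (SD 2) | Pooled SE | SE ratio | p, SD 2 | p, variance 2 |
|---|---|---|---|---|---|---|
| 8 | 48 | 0.0417 | 0.0593 | 1.42 | 0.043 | 0.039 |
| 15 | 41 | 0.0297 | 0.0514 | 1.23 | 0.020 | 0.019 |
| 20 | 36 | 0.0245 | 0.0486 | 1.16 | 0.014 | 0.013 |
| 30 | 26 | 0.0172 | 0.0454 | 1.08 | 0.008 | 0.008 |

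**Direction, with a baseline effect.** Trials were simulated under the planned effect (500 per scenario, 50 imputations). Assumptions: 30–70% of discontinuers with films, baseline log-odds effect of 0, −0.5 or −1.0 per SD, no slope covariate, 5% two-sided.
- The pooled SE exceeded the within-imputation SE by about 1.04 with 17 missing per arm, 1.09 with 28 and 1.19–1.20 with 39.
- The central cell was significant while the primary was not in 2.4–10.6% of all trials, or 12–35% of those with a non-significant primary.
- The reverse occurred in 0–6.8%, mainly with a strong baseline effect.

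**The case against.** The best defence is that each cell answers a conditional question. If exactly these missing patients were responders, nothing is missing and no between-imputation variance belongs in the test. Uncertainty about the fill is shown by the whole grid, worst case included, and readers then judge plausibility, as 5.4.3.1 intends. This stands as a defence of the grid as a display. It does not make the boundary the point where the pooled, adjusted conclusion is lost.

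Other points that stand:
- A reader might infer that, at the plan's own rates, the primary would miss 5% with 8 retrieved dropouts while the grid shows 0.004. That follows only if the SAP's priors are ignored (SE ratio 1.49, p about 0.055). With them p is about 0.04. That exceeds 0.025, which matters only if the other dose fails at 0.05. The other three cases stay below 0.025.
- Eight is the extreme. With fewer in any arm, SAP 2.5.3 drops treatment from the imputation model. Protocol section 6 asks for final films from discontinued patients, and the documents give no expected number.
- The calculations omit the post-baseline slope. Any predictive value it has would reduce the imputation variance.
- A reader might infer that the grid always errs towards robustness. It does not: leaving out a prognostic covariate tends to cost power, and the simulation found reversals.
- SAP 2.5.4 also allows covariate-adjusted analyses and the unused imputation models, though both are optional. The optional logistic model in 5.4.3.1 restores the covariate for some cells but not the missing variance.

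**Conclusion.** The point holds as a limited one. The binary grid is a legitimate display, but it is not tied to the primary analysis and its boundary does not mark where the trial's conclusion changes. The gap is small when few films are missing. It grows as missing films increase and retrieved dropouts become fewer, and its direction depends on those numbers and on how prognostic baseline mSASSS is. In the assumed example it is p = 0.026 against about 0.06, or tipping at 8 against about 12 of 39. These sizes rest on assumed missing and retrieved counts, all missing films coming from discontinuers, and no covariate or slope effect.

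A reader might infer that the primary inference or its type I error is compromised. The documents do not support that: success is decided by the primary p-values through the Hochberg procedure (SAP 2.6.2), and the tipping point plays no part in it. This is a cheap improvement to a sensitivity analysis.

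**What to change.** Make the binary tipping point parallel to the continuous one:
- Add shifts d (secukinumab) and b (GP2017) to the imputation log-odds.
- Re-impute, rerun the baseline-adjusted logistic/Margins analysis in each completed dataset, and pool by Rubin's rules. With d = b = 0 this reproduces the primary result.
- Report the (d, b) pairs and implied response rates at which significance is lost, and state the significance level used.
- Apply the same to absence of new syndesmophytes.
- Keep the chi-square grid, labelled as descriptive.

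The prior scale should be made the same in 2.5.3 and 5.4.3.2, since the shifted analysis uses it. The cost is extra programming and run time; no new data are needed.

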### For continuous variables

Tipping point to compare each AIN group with the GP2017 group will be performed as follows:

- 1) For any patient  $i$  randomized to the AIN group with an imputed mSASSS value resulting in a change from baseline value in mSASSS at Week 104  $CB_{i,mSASSS}$ , let  $CB_{i,mSASSS}^{tipping} = CB_{i,mSASSS} + d$
- 2) For any patient  $j$  randomized to the GP2017 group with an imputed mSASSS value resulting in a change from baseline value in mSASSS at Week 104  $CB_{j,mSASSS}$ , let  $CB_{j,mSASSS}^{tipping} = CB_{j,mSASSS} + b$
- 3) Let  $d = -1, -2/3, -1/3, \dots, 2$  and  $b = -1, -2/3, -1/3, \dots, 2$

- 4) For each combination, repeat the same ANCOVA analysis with the same model used in the primary analysis and the newly computed changes from baseline
- 5) Identify the values of  $d$  and  $b$  that reverts significance
- 6) A different range of values for  $d$  and  $b$  can be used if no tipping point was identified or if it helps the clinical interpretation

#### 5.4.3.2 Multiple Imputation

A linear regression model will be used to perform multiple imputation (MI) under a missing-at-random (MAR) assumption. To help preserve the relationship between outcome and covariates within each treatment a separate model will be run for each treatment. This will also help ensure that the imputation model does not make stronger assumptions on data relations than the analysis model.

The SAS code below outlines a template for the analysis where covariates and visits can be added or removed as required. To ensure that results can be replicated the data should be sorted by subject number before running the model (the data should be in horizontal format with one subject per dataset row).

```
proc mi data= seed=4572340 nimpute=100 out=mi_out;  
by treatment;  
fcs reg (/details);  
var value1 value2 value3;  
run;
```

Where in the template code the continuous variable to be imputed is *value* (e.g., *value1* could be the baseline value and *value2* the first post-treatment measurement of the variable to be imputed.) Normally, all data collection visits during the analysis period of interest would be included in the model. Including variables using a CLASS statement instead of a BY statement should help facilitate model convergence also when the number of non-missing data points are low for some specific covariate level and visit combination. The FCS option is used to ensure that also non-monotone missing data can be handled in an appropriate way.

For a situation where several variables need to be imputed using separate models (e.g., using independent models to impute each component needed to derive a response variable  $V$ ) a step-wise process needs to be implemented as outlined below:

1. Run the SAS code as described above for the first variable to be imputed
2. Run the SAS code as described above for the next variable to be imputed (but with the following changes: “*data=mi\_out*”, “*out=mi\_out2*”, “*by treatment \_imputation\_*”, “*nimpute=1*”)
3. Repeat step 2, but with input dataset equal to the output dataset from the prior step, until all  $j$  variables have been imputed resulting in a dataset named *mi\_outj*
4. Derive the variable  $V$  from within *mi\_outj*

The required analysis (e.g., ANCOVA, logistic regression with Margins macro) is then performed separately within each imputation dataset (as identified by variable *\_imputation\_*).

To obtain the final result of the imputation process the analysis result from each imputation dataset needs to be combined according to Rubin's rules as outlined below:

```
ods output parameterestimates=mi_result;  
proc mianalyze data=;  
modeffects estimate;  
stderr estimate_se;  
run;
```

The *estimate* and *estimate\_se* parameters come from the analysis model used to analyze the imputed variable within each imputation dataset (e.g., from the lsmean estimate of the treatment difference and its standard error obtained from PROC LOGISTIC or PROC MIXED.)

To obtain binary response rates and confidence intervals for individual treatment groups the following process should be followed (exemplified for one visit):

```
ods output binomialprop=bin_est;  
proc freq data=;  
by treatment_imputation_;  
table response / binomial (cl=wilson correct);  
run;
```

Then apply a logit transformation on the saved proportions and derive its standard error:

```
data bin_est; set bin_est;  
estimate=log(_bin_/(1-_bin_));  
estimate_se=e_bin_/(_bin_*(1-_bin_));  
run;
```

The transformed binomial proportion estimates and its standard errors are then combined by applying Rubin's rules as described above using PROC MIANALYZE. Before presenting the combined data it needs to be transformed back as follows:

```
data mi_result; set mi_result;  
prop_est=1/(1+exp(-estimate));  
prop_lower=1/(1+exp(-lclmean));  
prop_upper=1/(1+exp(-uclmean));  
run;
```

If all responses are imputed as 0 (or 1) for all imputation datasets for a specific treatment group then the between-imputation-variation will be zero. The combined final response rate would be presented as seen in any of the imputed datasets but the 95% CI will be undefined.

If after imputation all responses are either 0 or 1 for a combination of treatment group and imputation dataset it will not be possible to perform a logit transformation and the response rate (0% or 100%) will be presented without 95% CI.

For the datasets generated with the PROC MCMC routine, the same analysis as described in this section will be performed. PROC MCMC will be run twice with 100000 iterations, a thinning of 1000, and burn-in of 10000 in order to obtain 200 partially completed datasets. 100 datasets will have imputed data for subjects who discontinued the study, and the other 100 datasets will have imputed data for subjects with missing data for other reasons (e.g., due to an incomplete number of interpretable locations). The two sets of 100 partially completed datasets will be patched together matching their iteration number. That is, the datasets corresponding to the  $i$ -th iteration of the first 100 datasets will be merged with the datasets corresponding to the  $i$ -th iteration of the second 100 datasets. The SAS code below outlines a template for the procedure:

```
PROC MCMC data= seed=4572340 nbi=10000 nmc=100000 thin=1000
missing=CCMODEL;
    parms beta1 beta2 beta3 beta4 beta5;
    prior beta1 beta2 beta3 ~ normal(0,var=2);
    prior beta4 beta5 ~ normal(0,var=3);
    pi = logistic(beta1 * trt_GP2017 + beta2 * trt_SEC150 + beta3 * trt_SEC300 + beta4 *
sqrt(base_stand) + beta5 * slope_stand);
    model y ~ binary(pi);
    preddist outpred=;
run;
```

Analogous codes will be used to impute the missing data due to other reasons (other than study discontinuation) as well as the change from baseline in mSASSS at Week 104 (secondary endpoint).

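### The SAP's template for arm-level response rates after imputation names no event level and uses crude proportions, although the logistic section fixes the event at 1 and defines arm rates by standardization: a minor reporting-code error.

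*SAP*

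**What the plan says.** Two parts of the SAP appendix describe how an arm-level response rate is obtained.

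- **SAP 5.4.2.2 (Logistic regression)** uses marginal standardization for the arm rates and for their difference: "Averaging these predictions for each treatment group provides the estimate of the mean response rate for each treatment group". The difference is then taken between those standardized rates. The Margins template fixes the event level with "roptions = event='1".
- **SAP 5.4.3.2 (Multiple Imputation)** gives a separate recipe: "To obtain binary response rates and confidence intervals for individual treatment groups the following process should be followed (exemplified for one visit". The recipe is PROC FREQ by treatment and imputation, with "table response / binomial (cl=wilson correct". The proportion and its standard error are put on the logit scale, pooled with PROC MIANALYZE and transformed back. No covariate and no event level appear.

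The 0/1 coding is visible in the same section ("If all responses are imputed as 0 (or 1) for all imputation datasets for a specific treatment group"), as is the intended quantity ("the response rate (0% or 100%) will be presented without 95% CI"). The recipe reaches the primary endpoint through this sentence: "For the datasets generated with the PROC MCMC routine, the same analysis as described in this section will be performed". SAP 2.5.3 also says that the response rate is calculated in each completed dataset and pooled by Rubin's rules.

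For the treatment effect, 5.4.3.2 asks for the required analysis in each completed dataset and names logistic regression with the Margins macro as an example. The comment on the pooling code then gives a different example, an estimate "from the lsmean estimate of the treatment difference and its standard error obtained from PROC LOGISTIC or PROC MIXED".

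**The concern.** The step that tests the hypothesis names its event level, but the step that produces the displayed rates does not. If the software default is the lower level, the proportion, its standard error, the logit and the confidence limits all belong to subjects who did progress. The arm rates in a no-progression table would then run against the tested difference beside them.

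The second problem remains once the level is right. The tested difference is adjusted for baseline mSASSS (SAP 2.5.2), while the PROC FREQ rates are not. The SAP gives two methods for the same arm rate and does not say which one is displayed. A reader who subtracts the printed rates may not recover the printed difference.

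At stake is the internal consistency of the headline results display, not the test.

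**Working it through.** **Inputs**

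- From SAP section 3: 63% no progression on secukinumab, 51% on GP2017, 279 per arm, α = 0.025 per dose, stated power about 73% per dose and 88% for at least one dose.
- Assumed, because the documents do not give them: (a) PROC FREQ tabulates the first ordered level when none is named; (b) the strength of the association between baseline mSASSS and response, taken as log-odds 0.3, 0.6 and 1.0 per SD with a normal covariate.

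**The plan's own figures**

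- Blended rate: 0.8 × 66% + 0.2 × 51% = 63.0%, as stated.
- SE under the null, pooled rate 0.57: √(2 × 0.57 × 0.43 / 279) = 0.0419. SE under the alternative: √((0.63 × 0.37 + 0.51 × 0.49) / 279) = 0.0416.
- Power: Φ((0.12 − 2.241 × 0.0419) / 0.0416) = 73.4%, against about 73% stated.
- At least one dose by Hochberg (2,000,000 draws, correlation 0.517 from the shared control): 87.6%, against 88% stated.

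The planning figures reproduce, so they are a fair basis for illustration.

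**Event level**

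The SAP's steps were applied to complete data with n = 279: logit(p) ± 1.96 / √(n p(1 − p)), then back-transformed.

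| Arm | Level 1 (no progression) | Level 0 (progression) |
|---|---|---|
| Secukinumab | logit 0.532, SE 0.124: 63.0% (57.2 to 68.5) | 37.0% (31.5 to 42.8) |
| GP2017 | logit 0.040, SE 0.120: 51.0% (45.1 to 56.8) | 49.0% (43.2 to 54.9) |
| Difference | +12 points | −12 points |

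The level-0 results are exact mirror images. No information is lost, but the display is the complement of the endpoint.

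**Crude against standardized**

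The chance imbalance in mean baseline between two arms has SD √(2/279) = 0.085 SD units. The average p(1 − p) is (0.2331 + 0.2499) / 2 = 0.2415, so a log-odds b per SD moves the difference by roughly 0.085 × 0.2415 × b. That is 0.6, 1.2 and 2.0 points for b = 0.3, 0.6 and 1.0. The approximation runs high for large b, because the slope averaged over subjects is flatter. Simulation (1,500 trials of 3 × 279 for each b) gives:

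| b | Mean gap (points) | SD of gap (points) | 95% of trials within (points) |
|---|---|---|---|
| 0.3 | 0.01 | 0.6 | 1.3 |
| 0.6 | 0.02 | 1.1 | 2.2 |
| 1.0 | 0.02 | 1.7 | 3.3 |

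The mean gap is essentially zero. The single-trial gap is well below the standard error of the difference itself, about 4.2 points.

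**What the PROC FREQ step feeds**

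The difference, its confidence interval and its p-value come from the Margins model in each completed dataset, pooled by Rubin's rules (SAP 2.5.2, 5.4.2.2, 5.4.3.2). The PROC FREQ output enters none of them.

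**The case against.** The strongest reply is that this is template code with an obvious purpose. Dataset names are left blank, the recipe is exemplified for one visit, and the surrounding text speaks of response rates throughout. A programmer completing it could set the level, and a table with the wrong sign should fail its first check. All of this stands. A reader might infer that the primary table will show non-response rates. The documents do not support that: it needs a software default they do not state, literal execution, and no one noticing. What remains is that the step is given as the process to follow and omits a specification that the neighbouring step includes.

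On the second part, observed arm rates beside an adjusted difference are common and acceptable if labelled. That also stands, but here the rates are not labelled, and 5.4.2.2 assigns the same quantity to standardization.

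A reader might also infer from the PROC LOGISTIC example that a log odds ratio will be pooled in place of the estimand. At the planning rates that would be ln(0.63/0.37) − ln(0.51/0.49) = 0.49, against a difference of 0.12. The documents do not support this either. The wording is a parenthetical example covering several procedures, the same section names the Margins macro as the analysis, and SAP 2.5.1 and 2.5.2 fix the summary as a difference in proportions. It is a loose example that merits alignment only.

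**Conclusion.** The point holds as a minor reporting-code error with two parts. First, the BINOMIAL option lacks an event level. Under the assumed default, 63% and 51% would print as 37% and 49%, with mirrored intervals. Second, the arm rate has two definitions. The displayed rates may miss the tested difference by typically 0.6 to 1.7 points in a single trial, under the assumed covariate strengths and without expected bias.

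It would be wrong to read this as a threat to the primary result. The primary estimate, p-value, multiplicity control and power do not pass through the step. No table shell is available in the documents, so which rate will be displayed is itself an inference from the code.

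**What to change.** In SAP 5.4.3.2:

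1. Add `level='1'` to the BINOMIAL option.
2. State that the arm rates shown beside the tested difference are the Margins rates from each completed dataset, pooled by Rubin's rules, with the logit scale used for their confidence intervals.
3. If the PROC FREQ rates are kept, label them as crude (unadjusted).
4. As an editorial alignment only, cite the Margins difference and its standard error, in place of PROC LOGISTIC, as the example input to PROC MIANALYZE for binary endpoints.

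The cost is a few lines of template text before database lock. No new data, design change or change to the tested analysis is needed.
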